13.4 Analysis of Secondary & Exploratory Endpoints

Secondary endpoints include biochemical (PSA) response rate, duration of PSA response, biochemical (PSA) progression, time to biochemical (PSA) progression, time to biochemical (PSA) progression above baseline, overall survival, and toxicity. We anticipate that the 95% confidence interval around the PSA response rate will be within $\pm 9\%$ of the true value for Arm 1 and within $\pm 15\%$ of the true value for Arm 2. Time to biochemical (PSA) progression, time to biochemical (PSA) progression above baseline, median MFS-time, and overall survival will be estimated using the Kaplan-Meier method, and 95% confidence intervals will be calculated using Greenwood's formula.

The frequency of subjects experiencing toxicities will be tabulated. Toxicities will be assessed and graded according to CTCAE v. 4.0 terminology. Exact 95% confidence intervals around the toxicity proportions will be calculated to assess the precision of the obtained estimates.

Imaging studies: The possibility of identifying sites of metastatic disease not apparent on conventional imaging (CT/MRI abdomen/pelvis, bone scan, and CXR) will be confirmed with serial imaging. Any potential metastatic site on J591 imaging will be followed over time by conventional imaging. Sites of disease appearing on J591 scan and subsequently confirmed by conventional imaging will be labeled as positive. Any site apparent on J591 scan that is subsequently biopsied as part of standard care and confirmed to be metastatic prostate cancer will be labeled as definite. Sites of disease appearing on J591 scan without any corroborating evidence (conventional imaging or biopsy) will be labeled as possible.

Adrenal hormonal levels: Baseline adrenal hormonal levels will be categorized by median baseline levels found in CALGB 9583 (60, 61). In addition, as this may be a different patient population, we will analyze by median as well as quartiles. We will correlate levels with time to radiographic metastatic disease as well as PSA response and overall survival. Changes in adrenal hormone levels will be analyzed with time (baseline, 1 month, 6 months, at progression).

Plasma markers of hemostasis/fibrinolysis/angiogenesis: Baseline levels will be categorically analyzed by median as well as in quartiles and will be correlated with clinical endpoints (time to mets, survival, PSA response). We will also perform exploratory analyses using these values as continuous variables. In addition, a description of changes in levels of these markers with time/treatment will be reported. We will explore changes (decreases) by 50% (and median decrease) in correlation with outcome/response.

CTC's: Change in CTC counts will be summarized descriptively. Baseline counts ≥ 5 CTCs vs < 5 (per 7.5 mL) will be analyzed for time to metastatic disease in the overall population. We will also analyze changes with therapy: Decrease from ≥ 5 to < 5 , increase from < 5 to ≥ 5 , and stable categorical counts with respect to primary and secondary efficacy endpoints.

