A subsequent multicenter phase I/II study was initiated based upon the above results (50). Sixty two subjects received multiple doses of MLN2704. Because of neurotoxicity at every 1 or 2 week doses, the study was amended to include every 3 week dosing and dosing on days 1 and 15 of 42-day cycles. Of the 4 schedules tested, PSA declines were most frequent at 330 mg/m² every 2 weeks (2/6 had PSA decrease $>50\%$, 2/6 had PSA stabilization). However, grade 2-3 neuropathy was dose-limiting, and could not be predicted by prior taxane-based chemotherapy, diabetes, or prior neuropathy. Although response was modest, and treatment was limited by toxicity, this trial demonstrated proof of principle that an immunoconjugate utilizing a PSMA antibody has therapeutic potential.

Phase II trial of ¹⁷⁷Lu-J591 in metastatic castrate resistant prostate cancer

Based upon the phase I results described above (47), a phase II trial has completed enrollment. In this investigator-initiated study, subjects with progressive metastatic CRPC received one dose of ¹⁷⁷Lu -J591 in two-cohorts. Cohort 1 (65mCi/m²), 15 pts; Cohort 2: (70mCi/m²), 17 pts. The primary endpoint is PSA and/or measurable disease response; the secondary endpoint is toxicity. A ¹⁷⁷Lu-J591 imaging study was done to confirm tumor targeting.

All of the initially planned 32 pts (14 chemo-naïve) have been treated. Preliminary analysis reveals the following (51):

Median age is 71 (range 51 – 88), median baseline PSA 77.92 (range 3.31 – 2184.6). Three pts achieved PSA declines of >50%. Another more preliminary analysis has been performed based upon retrospective analyses in patients on prospective chemotherapy trials demonstrating that 30% declines in PSA are most associated with survival benefits (52, 53). Of the 15 subjects receiving 65mCi/m², 2 of 15 (13%) achieved a 30% PSA decline. Of the 17 subjects receiving 70mCi/m², 7 (47%) experienced at least a 30% decrease in PSA.

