11.2 Response Criteria

11.2.1 Biochemical (PSA) response

A PSA decline of $\geq 50\%$ has been demonstrated to correlate with improved survival in advanced castrate disease (119). In addition, Scher, et al have demonstrated that a PSA which either declines or shows no increase from baseline at either 8 or 12 weeks after initiating therapy correlates with improved survival compared to patients whose PSA rises despite therapy (120). Both of these criteria ($\geq 50\%$ PSA decline and no increase from baseline) will be recorded.

PSA response will be determined by comparing the PSA levels after therapy to the baseline, pre-treatment PSA. A decline of $\geq 50\%$, confirmed by a second PSA value ≥ 2 weeks later, should be reported. Patients must not demonstrate clinical or radiographic (CT and/or MR) evidence of disease progression during this time period.

Analyses of phase III trials of docetaxel versus mitoxantrone chemotherapy in men with metastatic androgen independent prostate cancer have shown that a 30% decrease in PSA levels is most strongly associated with a treatment effect on overall survival (52, 53). A PSA decline of $\geq 30\%$ will be assessed and used for exploratory analysis in the prediction of time to metastatic disease and overall survival.

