13. STATISTICAL CONSIDERATIONS

13.1 Study Design/Endpoints

The study is a randomized phase 2 study with a 2:1 ratio favoring ^{177}Lu -J591, with stratification by investigational site and mode of primary therapy (radiation vs surgery). Randomization will be performed by using a series of randomized blocks of 6 within each participating site/primary therapy stratum (with a 2:1 allocation ratio). This will provide assurance that after six patients are enrolled in any given participating site/primary therapy stratum, there will be four patients assigned to the combination regimen (Group 1) and two patients assigned to the single regimen (Group 2). This procedure will allow for each site to contribute similar numbers of ^{177}Lu -J591/ketoconazole patients and ^{111}In -J591 (placebo)/ketoconazole patients within the defined participating site/primary therapy strata.

The primary endpoint is the proportion free of metastases in each group at 18 months. Ninety-five percent confidence intervals (95% CI) will be estimated for the 18-month MFS proportion in both groups via binomial proportions. The MFS proportion will also be descriptively evaluated at 12, 24, 30, and 36 months in each group.

MFS will be measured from the start of the treatment to the date of either documentation of metastatic disease or death. All treated patients will be observed for a minimum of 18 months. The 18-month MFS proportion with ketoconazole + ^{111}In -J591 has been estimated to be 50% {521 Smith, M.R. 2005}; therefore, the target 18-month MFS proportion for the combination of ketoconazole + ^{177}Lu -J591 regimen is hypothesized to be 80%. An intent to treat analysis will include all randomized subjects. However, we will also analyze subjects who received study-drug. This subset will be those subjects who met eligibility requirements, have initiated therapy, and were not removed from the study for non-compliance or patient withdrawal within the first 4 weeks, and received infusion of study drug.

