With approximately 34 patients in the ketoconazole+J591 arm and 17 patients in the ketoconazole monotherapy arm (2:1 allocation), this design will allow for the detection of a 30% absolute difference in the 18-month MFS proportion between the ketoconazole+J591 arm and the ketoconazole monotherapy arm (80% vs. 50%, respectively) with $\geq 80\%$ power and a one-sided alpha level of 10%. An additional 10% will be enrolled to account for loss to follow up (total projected number of subjects to be randomized = 55). A 95% CI for the difference in the 18-month MFS proportion between the two treatment arms can be constructed to be within $\pm 18\%$ of the true difference in 18-month MFS proportions.

13.1.1 ^{111}In -J591 as placebo

We have chosen to infuse ^{111}In -J591 as a placebo in this double-blind study. The infusion procedures and characteristics of this compound are similar to ^{177}Lu -J591. In addition, ^{111}In -J591 will allow imaging studies to be performed. Because ^{111}In is a pure gamma-emitter, there will be no treatment effect as in the beta emission with ^{177}Lu . It is theoretically possible that by infusing ^{111}In -J591, there will be a treatment effect by ADCC, thereby diluting the proportional effect of ^{177}Lu -J591 in the experimental arm. However, clinically meaningful ADCC is not expected, as it has been demonstrated at

much higher doses of the J591 antibody (122), and by giving equal antibody doses in each study arm, we will be able to truly evaluate the effect of ^{177}Lu radioimmunotherapy.

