13.2 Sample Size/Accrual Rate

The planned sample size is 55 subjects ($50 + 10\%$ for in-evaluable / loss to follow-up = 55). Subjects who come off protocol prior to day 29 of treatment (i.e. prior to infusion of study drug) will be replaced. It is anticipated that the average site will pre-screen several subjects per month and enroll approximately 3 subjects per year.

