13.5 Reporting and Exclusions

- 13.5.1 **Evaluation of toxicity.** All patients will be evaluable for toxicity from the time of their first treatment on study. Toxicity of radiolabeled J591 in this population will be evaluated from the time of J591 administration.
- 13.5.2 **Evaluation of response.** All patients included in the study will be assessed for response to treatment if they have received at least 4 weeks of therapy with ketoconazole and received radiolabeled J591. Subjects dropping out of the study prior to J591 administration will be replaced.

14 Inclusion of Women and Minorities

Women are excluded from the protocol because prostate cancer is a disease of men. No exclusion based upon race/ethnicity will occur.

15. Study Personnel

Study Chair ([name]): Responsible for patient recruitment and over-all clinical management, protocol design and coordination, assessment of adverse events, safety, toxicity, and effect of treatment. Will communicate with principal investigators and study personnel at all sites and run monthly study teleconferences with the Study Coordinator. Will oversee any changes to the protocol and will be responsible for submitting amendments to the appropriate regulatory agencies (such as IRB, DSMB, sponsors, FDA, etc.). [See also Appendix D]

WCMC Co-Investigators ([name], [name], NP, [name], [name], [name], [name] NP, [name]): Responsible for patient recruitment, overall clinical management, assessment of adverse events, safety, toxicity, and effect of treatment. Will assist with protocol design, coordination, and interpretation of scans.

Nuclear Medicine Chairs ([name], [name]): Responsible for administration of IND agents (radiolabeled J591 antibodies) for diagnostic and therapeutic studies, will oversee evaluation and quantitation of radiolabeled J591 scans. Will oversee quality control of radiolabeled antibody.

Statistician ([name], MS, Dr.PH): Assist with study design, data analysis and interpretation, assist with protocol amendments.

Research Nurse Assist with patient recruitment, study drug administration, documentation of adverse events.

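### The 95% confidence interval widths stated for PSA response (±9 points in Arm 1, ±15 in Arm 2) need very low or very high response rates with 34 and 17 men; at 20–50% response they overstate precision

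*Combined protocol and SAP*

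**What the plan says.** Section 13.4 lists PSA response rate first among the secondary endpoints and says "We anticipate that the 95% confidence interval around the PSA response rate will be within" a fixed margin: 9 percentage points for Arm 1 and 15 for Arm 2, measured from the true value. It names exact intervals for the toxicity proportions but no method for PSA response, and it states no expected response rate.

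The arm sizes are in Section 13.1: "With approximately 34 patients in the ketoconazole+J591 arm and 17 patients in the ketoconazole monotherapy arm (2:1 allocation"). The same section numbers the groups: in each block of six, "there will be four patients assigned to the combination regimen (Group 1) and two patients assigned to the single regimen (Group 2"). Arm 1 is therefore read here as the larger, ¹⁷⁷Lu-J591 arm. Section 13.2 adds an allowance for loss: "The planned sample size is 55 subjects". Section 13.5.2 assesses men for response "if they have received at least 4 weeks of therapy with ketoconazole and received radiolabeled J591", and replaces those who leave earlier. Section 11.2.1 defines response as a PSA fall of at least 50%, "confirmed by a second PSA value" at least two weeks later.

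**The concern.** A 95% interval of ±9 points around a proportion from 34 men is narrow. Half-width is largest at 50% response and shrinks only towards 0% or 100%, so the statement holds only for extreme rates, and the plan names none. The sentence is also the plan's only statement of how precisely the response rate will be estimated. A reader who relies on it would expect a tighter estimate, and an easier comparison with other PSA response data, than the trial is likely to give.

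**Working it through.** **Inputs.** n = 34 and 17 (Section 13.1); 37 and 18 if all 55 randomised men are counted at 2:1 (Section 13.2). Stated 95% half-widths are 0.09 and 0.15 (Section 13.4). The response rate p is not given, so it is varied.

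**Arm sizes.** The primary calculation reproduces. With 80% vs 50%, one-sided alpha of 10% and a pooled null variance, the average proportion is (34 × 0.8 + 17 × 0.5)/51 = 0.70. The null SE is √[0.21 × (1/34 + 1/17)] = 0.136 and the alternative SE is √(0.16/34 + 0.25/17) = 0.139. Power is Φ[(0.30 − 1.282 × 0.136)/0.139] ≈ 0.816. So 34 and 17 are the right sizes to use.

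**The stated widths.** Half-width = 1.96 × √[p(1 − p)/n]. Solving for p:

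- Arm 1: p(1 − p) = (0.09/1.96)² × 34 = 0.0717, so p ≤ 7.8% or p ≥ 92.2%.
- Arm 2: p(1 − p) = (0.15/1.96)² × 17 = 0.0996, so p ≤ 11.2% or p ≥ 88.8%.
- With 37 and 18 men the lower limits move only to 8.5% and 12.0%.

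With exact (Clopper-Pearson) intervals, the low-end widths are met only with 1/34 or fewer and 1/17 or fewer responders; 2/34 gives a half-length of 9.5 points and 2/17 gives 17.5.

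**Widths the design delivers (Wald, 95%).** The first two rows use the protocol's single-agent ¹⁷⁷Lu-J591 results in Section 2.1: the phase II trial ("Three pts achieved PSA declines of >50"%, of 32 treated) and the phase I trial (4 of 35). The other rows are assumptions.

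| Response rate | Arm 1, n = 34 | ÷ 9 | Arm 2, n = 17 | ÷ 15 |
|---|---|---|---|---|
| 3/32 = 9.4% | ±9.8 | 1.09 | ±13.9 | 0.92 |
| 4/35 = 11.4% | ±10.7 | 1.19 | ±15.1 | 1.01 |
| 20% | ±13.4 | 1.49 | ±19.0 | 1.27 |
| 30% | ±15.4 | 1.71 | ±21.8 | 1.45 |
| 40% | ±16.5 | 1.83 | ±23.3 | 1.55 |
| 50% | ±16.8 | 1.87 | ±23.8 | 1.58 |

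Counting all 55 men gives ±14.8 and ±21.2 at 30%, and ±16.1 and ±23.1 at 50%.

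**Exact half-lengths over the same range.** Arm 1: 14.6 points at 7/34, 16.2 at 10/34, 17.6 at 17/34. Arm 2: 19.8 at 3/17, 22.8 at 5/17, 24.6 at 8/17. These intervals are asymmetric: 5/17 (29.4%) runs from 10.3% to 56.0%, so its upper limit lies 26.5 points above the estimate.

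**A possible origin (inference only).** With an 80% two-sided multiplier (1.282) and the MFS planning rates:

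- 80% with n = 34: 1.282 × √(0.16/34) = ±8.8.
- 50% with n = 17: 1.282 × √(0.25/17) = ±15.5 (±15.1 with n = 18).
- MFS difference, for which Section 13.1 states ±18% at 95%: 1.282 × 0.1393 = 17.9 points, against 1.96 × 0.1393 = 27.3 points at 95%.

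**The case against.** The sentence is a descriptive expectation for a secondary endpoint. No test, stopping rule or sample size uses it, and the reported interval will be computed from the data whatever it says. That stands, and it limits the severity.

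It can also be said that the sponsor may have had low response in mind. At the two ¹⁷⁷Lu-J591 rates the Arm 2 width is essentially met and Arm 1 misses by only 1 to 2 points. Section 2.1 also reports two men among 29 with PSA falls of 70% and 85% on ⁹⁰Y-J591. A rate of 2/29 = 6.9% would give 1.96 × √(0.069 × 0.931/34) = ±8.5 in Arm 1. But that is a different radionuclide in a dose-escalation study. All these trials lacked ketoconazole, and Sections 2.1 and 2.3 argue for possibly greater efficacy in minimal disease. Higher rates are therefore plausible, though the protocol gives none for either regimen: 20–50% is this review's assumption.

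Some stronger readings are tempting and do not hold:

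- That the widths can never be attained. They can, at the extreme rates shown.
- That precision is overstated almost twofold throughout. That fits only Arm 1 near 50% response; Arm 2 stays below 1.6 times.
- That the two widths contradict each other because 15/9 = 1.67 while √(34/17) = 1.41. That requires equal response in both arms, which the plan does not assume.
- That this interval is the only planned use of PSA response. Sections 2.4 and 13.4 also relate it to adrenal hormones, plasma markers and circulating tumour cells.

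**Conclusion.** The stated widths do not follow from 34 and 17 men at 95% confidence except at response rates of at most 7.8% or at least 92.2% (Arm 1) and at most 11.2% or at least 88.8% (Arm 2). Neither of the two rates the protocol gives for ¹⁷⁷Lu-J591 achieves ±9 in Arm 1. If response lies between 20% and 50%, precision is overstated by about 1.5–1.9 times in Arm 1 and 1.3–1.6 times in Arm 2. The conclusion does not depend on counting 51 or 55 men, or on Wald versus exact intervals. It does rest on reading Arm 1 as the larger arm.

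Severity is moderate: a stated figure needs correcting, but only the descriptive precision of a secondary endpoint is affected. A reader might infer that the trial is too small or that the primary analysis is compromised; the primary power calculation reproduces, so this point gives no ground for that. Nor do the documents establish that the 95% label is the mistake. The match with 80% intervals is close, but it uses MFS rates, not PSA rates.

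**What to change.** Replace the sentence in Section 13.4 with the widths the design delivers. State the response rates as assumptions and use one named method throughout. For example:

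> *Using exact (Clopper-Pearson) 95% intervals, as for toxicity, and assuming response rates of about 20–50%, the CI half-length will be about 15–18 points in Arm 1 (n = 34) and 20–25 points in Arm 2 (n = 17).*

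If the sponsor has its own planning rates, those should replace 20–50% and the widths be recomputed.

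The sponsor should also check the confidence level behind these figures and behind the ±18% for the MFS difference in Section 13.1. Relabelling the PSA widths as 80% would not be enough by itself: at 80% confidence ±9 with 34 men still needs response of at most 21.3% (or at least 78.7%), and ±15 with 17 men at most 36.9% (or at least 63.1%).

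The cost is one rewritten sentence and one check. No more men are needed and the primary analysis does not change; the stated precision becomes less favourable.

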5.1.3 Radiolabeled J591

Eligible patients will receive a single dose of ^{177}Lu -J591 (70 mCi/m²) or ^{111}In -J591 (5 mCi) on a Thursday or Friday approximately 4 weeks after cycle 1, day 1 consisting of J591 chelated at a specific activity of 12-15 mCi of ^{177}Lu per mg of antibody plus sufficient non-radiolabeled, non-DOTA-conjugated ("naked") J591 to achieve a total antibody dose of 20 mg. Each dose will be administered by an IV infusion at a rate not to exceed 5 mg/min.

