9.2 Special Studies

9.2.1 Radiolabeled-J591 Imaging

9.2.1.1 Assessment

9.2.1.1.1 Method of Assessment:

Planar imaging will be performed 2-8 days after radiolabeled-J591 administration (scan window will be assigned at randomization). In the case of a suspicious lesion, SPECT of the area may be performed at the nuclear med physician's discretion. In addition a CT/MRI may be obtained for possible confirmation. Identified sites will be followed on subsequent imaging modalities (bone scan, CT or MRI) to define the interval between identification of the lesion/s by radiolabeled-J591 versus other modalities. Images will be captured as specified in the Imaging Manual and provided to WCMC on disc in dicom format.

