¹ Baseline radiographic evaluation should be performed within one month of enrollment (or following enrollment as part of screening). Subsequent scans (CT/MRI abd/pelvis, CXR (or CT chest), and bone scan) should be performed every 6 months until PSA progression, then every three months thereafter unless clinically indicated sooner.

² CBC repeated twice a week when platelets <25,000/mm³ and/or ANC <500/mm³

³ CBC's not associated with study visits may be performed at any CLIA certified laboratory

⁴ The same lab should be used for all study PSA's if possible

⁵ CTC counts via CellSearch (using kit) at C1D1 prior to ketoconazole, C2D1 (prior to Lu-J591), C3D1, at the time of PSA progression, and at end of study. Additional blood samples for CTC analysis for research will be drawn at C1D1 prior to treatment and at end of study

⁶ Adrenal hormone levels should be drawn prior to starting treatment on Cycle 1, Day 1, 1 month, and at PSA progression

⁷ Starting after C1D1 assessment and blood draw until toxicity, investigator, or patient decision as per Sections 5.2.1, 5.2.2, 6.1. Distribute medication diary at the beginning of each cycle.

⁸ Visit 3 (C2D1): Targeted physical exams can be completed the day prior to the scheduled J591 infusion date.

⁹ All references to targeted physical exams throughout the protocol include a heart and lung examination, as well as evaluation of any abnormalities found during the complete physical exam performed at screening

¹⁰ Vital signs include temperature, heart rate, blood pressure, and respiratory rate.

¹¹ The End of Study Visit occurs when patient shows evidence of metastatic disease. Patient remains on trial until documented metastatic disease. In addition to scans a biopsy can be performed to prove metastatic disease. Patient can receive additional therapy prior to showing metastatic disease and still remain on trial. Site will be asked for information regarding the additional therapy in the case report forms.

¹² In the event that the J591 infusion is delayed, cycle 1 will be extended until the date of the J591 infusion. The date of the J591 infusion will be considered Cycle 2, Day 1.

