10.1 STUDY PROCEDURES: Schedule of Events

The assessments to be performed during the study are outlined below by study period, visit and day. Study assessments through Visit 9 (Day 85) will be completed within ± 3 days of the specified day for the visit, except where noted. Visits after Day 169 will be performed within ± 7 days of the scheduled visit.

Screening Period (Visit 1, Days -28 to -1) – All subjects

The procedures outlined for Visit 1 must be completed prior to the patient receiving study drug. The following procedures will be conducted at Visit 1:

- Informed Consent
- Medical History
- Concurrent medications
- Complete Physical Exam
- Vital Signs
- Demographics
- Previous therapy
 - Surgical report will include date and type of surgery +/- lymphadenectomy
 - Radiotherapy report will include modality of therapy with prescribed dose and field and dates of therapy
 - Previous hormonal therapy – drugs, doses, dates of therapy
 - Continuous vs intermittent therapy
- ECOG Performance Status
- Height, Weight
- CBC with differential and platelet count.
- PT or INR, PTT
- Electrolytes, BUN, Creatinine
- Total protein, albumin, calcium, total bilirubin, AST, ALT, LDH
- PSA
- PSA DT Calculation

- Alkaline phosphatase
- Testosterone
- Human anti-J591 antibody sample (may also be drawn C1D1 prior to initiation of study drugs)
- Urinalysis
- Archival Tissue (section 9.1.4) - Paraffin-embedded tumor blocks or 5 unstained slides with representative tumor tissue
- EKG, up to 1 month prior to treatment
- CT or MRI (abdomen-pelvis), up to 4 weeks prior to enrollment
- Bone scan, up to 4 weeks prior to enrollment
 - Any confirmatory tests to assess equivocal results of bone scan should also be completed within 4 weeks of enrollment
 - CXR, up to 4 weeks prior to enrollment (if CT chest has been performed within 4 weeks of enrollment, this procedure is waived)

Evaluations and procedures at Visit 2 (C1D1) – All subjects

Following screening procedures, eligible patients will be dosed with ketoconazole and hydrocortisone. See Section 5.1 for details on the dose and administration.

The following assessments are to be collected prior to drug administration unless otherwise noted:

- Interval medical history
- Targeted Physical Examination with vital signs
- ECOG PS
- CBC with differential and platelet count*
- Electrolytes, BUN, Creatinine*
- PSA*
- Adrenal hormone levels
- Plasma markers
- CTC's
- Adverse Events

- Concomitant medications

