- Electrolytes, BUN, Creatinine*
- PSA*
- Total protein, albumin, calcium, total bilirubin, AST, ALT, LDH
- Alkaline phosphatase
- Plasma markers
- Adrenal hormones
- CTC's
- Concomitant medications
- Concomitant/interval procedures
- Adverse events (pre- and post- infusion)

*Note that treatment day labs are used for radiolabeled-J591 baseline (not for assessment of eligibility)

Evaluations and procedures at Visit 4/J591 Scan (C2D3-9)

- Adverse Events
- Concomitant medications
- Concomitant/interval procedures
- J591 imaging (2-8 days after infusion). At selected study sites, whole body planar radionuclide images will be obtained between 2-8 days post-J591 treatment. The date of scan (3 or 4 days vs 6-8 days after J591 infusion) will be assigned at the time of randomization. SPECT studies of sites of disease will be obtained in selected patients as appropriate. These will be used to assess the ability of radiolabeled J591 to image

metastatic sites that do not appear on conventional imaging modalities (bone scan, CT/MRI).

Evaluations and procedures C2D22 (safety CBC for some subjects)

For subjects on aspirin/NSAIDs with anti-platelet properties or anticoagulation, a CBC on approximately Day 50 is **required** (3 weeks +/- 2 days after radiolabeled J591 infusion). For all other subjects, in particular subjects with baseline platelet counts < 200/mm³ a CBC at this timepoint is suggested, but not required.

- CBC with differential †

Evaluations and procedures C3D1

- Interval medical history
- Targeted Physical Examination
- Vital Signs
- ECOG Performance Status
- Verification of ketoconazole/hydrocortisone administration, Collection/Distribution of diary
- Adverse Events
- Concomitant medications
- Concomitant/interval procedures
- CBC with differential and platelet count.
- Electrolytes, BUN, Creatinine
- Total protein, albumin, calcium
- Total bilirubin, AST, ALT, alkaline phosphatase, LDH
- PSA
- Plasma markers
- CTCs

Evaluations and procedures Cycle 3 D8 *†

- CBC with differential and platelet count

Evaluations and procedures Cycle 3 D15 *†

- CBC with differential and platelet count†

Evaluations and procedures Cycle 3 D22 *†

- CBC with differential and platelet count†

All CBC results during cycle 3 must be either entered into the REDCap eCRF database or emailed to [contact] within 24 hours of testing.

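### The interval from J591 detection to conventional detection cannot be negative by design and largely reflects the scan calendar, so it should be reported as interval-censored and not as a lead time.

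*Combined protocol and SAP*

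**What the plan says.** The secondary objectives (1.2) include exploring whether J591 can image metastases in men with no disease on conventional scans. The Visit 4 procedures in 10.1 say the J591 images will be used to "assess the ability of radiolabeled J591 to image metastatic sites that do not appear on conventional imaging modalities". Section 13.4 states the analysis: "The possibility of identifying sites of metastatic disease not apparent on conventional imaging (CT/MRI abdomen/pelvis, bone scan, and CXR) will be confirmed with serial imaging".

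Follow-up under 13.4 starts from sites seen on J591. A site later confirmed by conventional imaging is labelled positive, a biopsy-proven site definite, and an uncorroborated site possible. Section 9.2.1.1.1 gives a further purpose for following these sites: "to define the interval between identification of the lesion/s by radiolabeled-J591 versus other modalities".

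Timing is set elsewhere:

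- **Conventional scans before treatment.** Section 3.1.4 requires them to be negative. Footnote 1 to the Study Calendar (section 10) says: "Baseline radiographic evaluation should be performed within one month of enrollment (or following enrollment as part of screening". The screening list in 10.1 has "Bone scan, up to 4 weeks prior to enrollment", with the same limit for CT/MRI and chest X-ray, and adds: "The procedures outlined for Visit 1 must be completed prior to the patient receiving study drug".
- **J591.** One infusion "approximately 4 weeks after cycle 1, day 1" (5.1.3), then one imaging session 2-8 days later (9.2.1.1.1).
- **Later conventional scans.** Footnote 1 says they "should be performed every 6 months until PSA progression, then every three months thereafter unless clinically indicated sooner". Under 11.2.3.1, a PSA rise in the first 12 weeks does not count as progression.
- **Unscheduled scans.** If J591 shows a suspicious lesion, 9.2.1.1.1 permits a CT/MRI. It is discretionary and has no time window, and bone scan is not named.

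**The concern.** A reader will take an interval between detection by J591 and detection by other modalities as a measure of how much earlier J591 sees disease. For that, the two modalities need a chance to see the lesion at about the same time, and the result must be able to fall either way.

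Neither condition is met. The conventional comparator predates the J591 scan by one to two months, and the next scheduled scan is months away. A lesion that becomes visible to both modalities between screening and the J591 scan is recorded as found by J591 first, and the recorded interval is the wait for the next conventional scan. Sites that J591 missed and conventional imaging found have no label in 13.4 and do not enter the interval. A published interval could then be read as earlier detection when it shows only when scans were booked.

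**Working it through.** The plan states no figure for this interval, so there is nothing to reproduce. The check is calendar arithmetic on the plan's own windows (no day 0; 1 month = 30.44 days), followed by an illustration.

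**1. Day of the J591 scan.** Infusion is at C2D1 = day 29. The scan at C2D3-9 falls on day 28 + 3 = 31 to 28 + 9 = 37.

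**2. Age of the conventional comparator.** Screening runs from day -28 to day -1.
- Shortest: day -1 to day 31 = 31 + 1 - 1 = 31 days.
- Longest: day -28 to day 37 = 37 + 28 - 1 = 64 days.

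The scan limit is tied to enrollment, so the age grows if C1D1 lags enrollment. For an assumed lag of 7-28 days the maximum is 28 + 7 + 36 = 71 to 28 + 28 + 36 = 92 days. Footnote 12 to the Study Calendar lets a delayed infusion extend cycle 1, which widens the gap further.

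**3. Wait for the next scheduled conventional scan.** The plan does not say where the 6-month clock starts.

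| Assumption | Scan day | Days after J591 | Months |
|---|---|---|---|
| 6 months from C1D1 | 184 | 184 - 37 = 147 to 184 - 31 = 153 | 4.8-5.0 |
| 6 months from a day -28 scan | 156 | 156 - 37 = 119 to 156 - 31 = 125 | 3.9-4.1 |
| PSA progression at 12 weeks, scan about 3 months from C1D1 | 92 | 92 - 37 = 55 to 92 - 31 = 61 | 1.8-2.0 |

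**4. What an equal tracer would show.** Suppose J591 and conventional imaging can see a lesion from the same date, so the true lead is zero. A lesion emerging after screening and before day 31-37 is positive on J591 and is next looked for conventionally after one of the waits in step 3. The recorded interval is that wait, about 2-5 months. An optional CT/MRI or a scan prompted by symptoms could shorten it to days, but not below zero.

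**5. How many men.** The synopsis expects 50% of controls to have metastases at 18 months. With exponential onset (an assumption), the hazard is h = ln 2 / 18 = 0.0385 per month, and the share with a lesion emerging in the gap is 1 - exp(-h × gap).
- 31 days: 1 - exp(-0.0385 × 31/30.44) = 3.85%.
- 64 days: 1 - exp(-0.0385 × 64/30.44) = 7.8%.

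If all 50-55 men were imaged, that is 50 × 3.85% = 1.9 to 55 × 7.8% = 4.3 men. At the target of 80% metastasis-free, h = -ln(0.8)/18 and the shares are 1.3% and 2.6%. The counts are upper figures, because 10.1 places J591 imaging at selected sites only.

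**6. What correct limits look like.** Take an illustrative site with a negative screening scan on day -14, a J591 scan on day 34 and a positive conventional scan on day 184. Relative to J591, conventional detectability began somewhere between -(34 + 14 - 1) = -47 days and 184 - 34 = +150 days. That range includes zero, so the data do not show which modality could have seen the lesion first. A conventional scan negative at that site on day 40 would move the lower limit to +6 days, and only then is a positive lead supported.

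**The case against.** The strongest reply is that the plan makes no head-to-head claim. The labels in 13.4 grade how well a J591-positive site is corroborated and do not score order. Order enters only through a descriptive interval in 9.2.1.1.1, with no test or superiority claim attached, and the objective is exploratory. All of this stands, and it limits the weight of the point.

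Three stronger readings are tempting and are not supported:

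- **That the plan scores J591 as first every time.** J591 does precede conventional imaging at every J591-positive, later-confirmed site, but that follows from how those sites are selected. It does not apply to metastases arising after the J591 scan, which the interval leaves out.
- **That the imaging results cannot come out against J591.** They can. Uncorroborated sites stay possible, so many possible and few positive sites would be an unfavourable result. Only the interval is one-sided.
- **That the apparent lead is always close to five months.** That holds only for 6-monthly scans counted from C1D1. The 3-monthly schedule after PSA progression, scans done on clinical grounds and the optional CT/MRI can all shorten it.

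The optional CT/MRI does not cure the problem. It depends on discretion and is triggered only by a suspicious J591 finding. It can bring the interval towards zero but cannot reverse it.

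**Conclusion.** The concern holds for the interval in 9.2.1.1.1. Among J591-positive sites confirmed later it is non-negative by construction, and its length is largely the distance to the next conventional scan. A tracer equal to conventional imaging would show roughly 2-5 months of apparent lead unless an unscheduled scan came sooner. About 4-8% of imaged men at the control rate, at most about 2-4 men, would have a lesion emerge in the gap before the J591 scan. Few sites of any kind are likely, so even that number could be a sizeable part of the reported result.

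The day ranges rest on the plan's visit windows and on the assumed starting points of the 3- and 6-month clocks. The percentages rest on exponential onset at the planned rates. The primary endpoint, its error rate and power, and the safety analyses are untouched. This is a cheap improvement to a secondary, descriptive output.

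**What to change.** Change the wording of 9.2.1.1.1 and 13.4 as follows:

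- Report the interval as interval-censored, measured from the J591 scan date, and do not call it a lead time. For each J591-positive site, place conventional detectability between the last conventional scan negative at that site and the first one positive there.
- Where the last negative scan is the screening scan, give the lower limit its true negative value. Setting it to zero would restore the bias. Where no later scan is positive, leave the upper limit open.
- State for each site whether any conventional scan on or after the J591 date was negative there.
- From reads already collected, tabulate sites first seen on conventional imaging in men whose J591 scan was negative at that site. Show the time since the J591 scan, because many of these lesions will have arisen after it and are not misses.

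A rule forcing every site already positive on the first post-J591 scan into an undetermined-order class is not needed. It would require two conventional scans after J591, and the calendar schedules none once documented metastasis has ended the study for that man.

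The cost is wider and less favourable intervals and slightly more analysis work, with no added scan or reader. One limit remains: the method assumes that a lesion, once visible, stays visible. Treatment may break that assumption, particularly in the 177Lu arm, and the report should say so.
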